## Human Subjects Research Protocol

The Common Human Subjects Protocol Cover Form **must** be completed and **attached** to the front of this form. This Protocol form should be completed for any human subjects research proposal that does not have a specific "protocol," such as a grant application. This form must be submitted along with a copy of the complete grant proposal and all the information in this form **must** be consistent with that proposal. This protocol form, once IRB approved, will be the working protocol for that research. **When completing this document, do not refer to page numbers within your grant.** If revisions are necessary during the course of the research, amendments should refer to this protocol form, not the grant proposal. Enter responses for all sections. Check N/A if the section does not apply.

### PROTOCOL SUMMARY

Project Title:

Protocol Version Date:

The Nicotinic Cholinergic System and Cognitive Aging

Principal Investigator: [name].

Grant Sponsor: NIH/NIA

Grant Number: 30282

(For grants routed through UVM, indicate the OSP Proposal ID # located at the top of the OSP Routing Form)

**Lay Language Summary:** (Please use *non-technical* language that would be understood by nonscientific IRB members to summarize the proposed research project. The information must include: (1) a brief statement of the problem and related theory supporting the intent of the study, and (2) a brief but specific description of the procedure(s) involving the human subjects. Please do not exceed one single-spaced 8 1/2 X 11" page.)

Prior research has shown that a chemical system in the brain called the cholinergic system is the primarily responsible for cognitive symptoms seen in people with dementia. While therapeutic benefits are clear in dementia, what remains uncertain is the role that the cholinergic system in general and a subset of receptors called the nicotinic system plays in cognition in healthy non-demented older adults (referred to as normal cognitive aging). This is critical because the ever growing healthy aging population will show declines in cognition that fall short of dementia but still impact functional abilities and independence. In dementia structural changes in the nicotinic system appear to be related to cognitive dysfunction. However, in normal aging there is no evidence for structural changes in the nicotinic system but age-related functional differences exist. The preservation of structural aspects of the nicotinic system in normal aging implies that a manipulation to enhance nicotinic functioning may lessen the cognitive symptoms of aging. Understanding the effects of age-related functional changes on the nicotinic system will elucidate a critical neurobiological mechanism that may be responsible for age-related changes in cognition and will shed light on how nicotinic dysfunction precedes cognitive dysfunction in normal aging. As the search continues for safe and effective cognitive enhancers, it will be important to understand the role of the nicotinic system in cognitive aging and whether nicotinic mechanisms have the potential to benefit cognition in healthy adults.

We propose that the functioning of the nicotinic system is affected by normal aging, is involved in the increase in frontal activation seen for older compared to younger adults, and therefore can be manipulated to model "older" and "younger" patterns of performance and brain activation.

Older adults (aged 65-75 years) and younger adults (aged 21-30 years) will participate in a screening visit and then three (3) nicotinic challenge study days which include performing a working memory task during functional magnetic resonance imaging (fMRI). The nicotinic challenges will consist of 1) 20 mg oral mecamylamine, 2) 7 mg transdermal nicotine, and 3) matching placebos. After an extensive medical, behavioral, and cognitive screening we will enroll and complete 48 older adults and 48 younger adults.

## **PURPOSE AND OBJECTIVES**

**Purpose:** The importance of the research and the potential knowledge to be gained should be explained in detail. Give background information.

Prior research has shown that the cholinergic system is the primary neurotransmitter system responsible for cognitive symptoms in dementia (Bartus et al. 1982). The cholinergic hypothesis of geriatric memory dysfunction (Bartus et al. 1982) hypothesizes that functional disturbances in cholinergic activity occur in the brains of demented patients and that these disturbances play a role in memory loss and related cognitive problems. This hypothesis has been supported by the finding that cholinesterase inhibitors show positive effects on cognition in Alzheimer's disease (AD) patients (e.g., Hansen et al. 2008) and nicotine administration improves attention and memory in patients with Mild Cognitive Impairment (MCI; [name] et al. 2012). Much clinical development research on cholinergic agents has followed since the initial proposal and although the overall clinical effects are limited, the cognitive enhancers that modulate cholinergic functioning remain the most widely used medications that have been approved for use in AD.

While therapeutic benefits are clear in dementia, what remains uncertain is the role that the cholinergic system in general and the nicotinic system specifically plays in cognition in healthy non-demented older adults (referred to as normal cognitive aging in this application). This is critical because the ever growing healthy aging population will nonetheless show declines in cognition that fall short of dementia but still impact functional abilities and independence (Blazer et al. 2015). The goal of successful aging is to maintain intact cognitive functioning all the way until death. Since Bartus' original proposal there have been significant advances in understanding how changes in the nicotinic cholinergic system occur in pathological aging and to a lesser extent with normal aging to affect cognition. Specifically, nicotinic systems are involved in attention and other cognitive processes to the extent that they require effortful processing like working memory (e.g. Warburton & Rusted 1993). In dementia structural changes in the nicotinic system appear to be related to cognitive dysfunction (Picciotto & Zoli 2002). However, in normal aging there is no evidence for structural changes in the nicotinic system but age-related functional differences exist (Decker 1987). *The preservation of structural aspects of the nicotinic system in normal aging implies that a manipulation to enhance nicotinic functioning may lessen the cognitive symptoms of aging.* More recently, with the increased use of brain functional magnetic resonance imaging (fMRI) in combination with psychopharmacological probes, data patterns have emerged that further define the role of the nicotinic system in cognition, aging, and dementia. Understanding the effects of age-related functional changes on the nicotinic system will elucidate a critical neurobiological mechanism that may be responsible for age-related changes in cognition and will shed light on how nicotinic dysfunction precedes cognitive dysfunction in normal aging. *As the search continues for safe and effective cognitive enhancers, it will be important to understand the role of the nicotinic system in cognitive aging and whether nicotinic mechanisms have the potential to benefit cognition in healthy adults.*

**References.** Include references to prior human or animal research and references that are relevant to the design and conduct of the study.

- Baddeley AD (1986) Working Memory. Oxford: Clarendon Press.

## METHODS AND PROCEDURES

**Study Design:** Describe the research design, including a description of any new methodology and its advantage over existing methodologies.

**Design:** Older adults (aged 65-75 years) and younger adults (aged 21-30 years) will participate in a screening visit and then three (3) nicotinic challenge study days which include performing a working memory task during fMRI. The nicotinic challenges will consist of 1) 20 mg oral mecamylamine, 2) 7 mg transdermal nicotine, and 3) matching placebos. After an extensive medical, behavioral, and cognitive screening we will enroll and complete 48 older adults and 48 younger adults.

**Procedures:** Describe all procedures (sequentially) to which human participants will be subjected. Identify all procedures that are considered experimental and/or procedures performed exclusively for research purposes. Describe the types, frequency and duration of tests, study visits, interviews, questionnaires, etc. Include required screening procedures performed before enrollment and while on study. Please provide in table, list or outline format for ease of review. (describe and attach all instruments)

Note: A clinical research protocol may involve interventions that are strictly experimental or it may involve some aspect of research (e.g., randomization among standard treatments for collection and analysis of routine clinical data for research purposes). It is important for this section to distinguish between interventions that are experimental and/or carried out for research purposes versus those procedures that are considered standard therapy. In addition, routine procedures performed solely for research purposes (e.g., additional diagnostic/follow-up tests) should be identified.

**Cognitive/Behavioral Screening:** All **older participants** will be cognitively and behaviorally assessed using standard tests designed to exclude participants with significant cognitive or behavioral impairment including the Mini Mental State Exam (MMSE) (Folstein et al. 1975), Brief Cognitive Rating Scale (Reisberg et al. 1993b), the Mattis Dementia Rating Scale (Jurica et al. 2001), and the Global Deterioration Scale (GDS) (Reisberg et al. 1993a). Participants will be required to have a GDS score of 1-2, a MMSE score of greater than or equal to 27, and score above 130 on the Mattis scale. Older participants will have an informant complete the Informant Questionnaire on Cognitive Decline in the Elderly (IQCODE; Jorm 2004) and have scores of 3 or less indicating no cognitive change.

All **older and younger participants** will undergo the following behavioral screening measures: a Structured Clinical Interview for DSM-IV-TR (SCID) (First et al. 2001) to establish the presence/absence of Axis I psychiatric disorders, and the Beck Depression Rating Scale (BDI, score < 10) (Beck et al. 1961). Participants will be excluded if they have a current Axis 1 disorder. All participants will perform the Wechsler Abbreviated Scale of Intelligence (WASI) to assess IQ and will be required to score above 80.

**Neuropsychological Screening:** In an effort to ensure the older adults are not at the beginning stages of MCI or dementia and to assess general neuropsychological functioning, **older and younger participants** will be screened with the **Repeatable Battery for the Assessment of Neuropsychological Status (RBANS)** (Randolph 1998). RBANS was developed for the dual purposes of identifying and characterizing abnormal cognitive decline in older adults and as a neuropsychological screening battery for younger adults. The RBANS assesses five cognitive domains including immediate memory, language, visuospatial/constructional ability, attention, and delayed memory and provides a global total measure. Each participant will need to score within one standard deviation (*SD*) of the mean for her/his age. A measure of executive functioning is missing from the RBANS so we will include selected measures from the **Delis-Kaplan Executive Function System (D-KEFS)**. Specifically we will include the Trail Making Test and Verbal Fluency subtests. All participants will be required to score within one *SD* of the mean for their age.

**Medical Screening:** Participants will be physically healthy **nonsmokers** with a BMI  $\leq 32 \text{ kg/m}^2$ , and no cardiovascular disease other than mild hypertension. Participants will be assessed by history, physical exam, and laboratory tests assessing cardiac, hematopoietic, renal, hepatic, and hormonal function (CBC, CMP, TSH, U/A, ECG), and will have a medical history review and physical examination to establish general physical health. Blood will also be obtained for an **exploratory genetic analysis** to examine APOE and COMT genotypes as these genes have been shown to be important in cognition in older adults. APOE is important for cognitive decline in older adults and associated with cholinergic function (Espeseth et al, 2006). The COMT ValMet polymorphism modulates working memory performance in psychiatric populations (e.g. Meyer-Lindenberg & Weinberger 2006) but not in healthy subjects (Blanchard et al. 2011). However, it affects working memory-related brain activation (Jacobs & D'Esposito 2011).

Depending on the distribution of genotypes we will use this information as a covariate in the imaging analysis described below.

Once a participant passes the screening, s/he will be scheduled for **3 challenge and fMRI study days**.

**Pharmacological Challenges:** These procedures used for the nAChR challenges are similar to the procedures used in our prior studies ([name] et al. 2008; 2010; 2012; Carstens et al. 2011; [name] et al. 2009; 2012). The nAChR antagonist mecamylamine (**MECA**) will be administered at a dose of 20 mg orally as the hydrochloride salt. Placebos will consist of identical capsules filled with lactose. This dose of MECA is the same dose used in our prior studies in older women ([name] et al. 2008; 2012). Nicotine (**NIC**) will be administered with a 7 mg patch placed on the back of the shoulder for 45 minutes. Matching placebo patches will be used. This dosing procedure has utilized at UVM for many years to study the acute effects of nicotine in nonsmokers (Carstens et al. 2011; [name] et al. 2009; 2012). One dose of MECA, NIC, and placebo will require three challenge days for each participant.

**Drug Challenge Procedures:** The three drug challenge days for each participant will be spread over no more than one month. No study day will follow a previous one by less than 48 hours. This time line has proven to be acceptable to participants for their time commitment to the study and does not negatively impact recruitment. The drug sequence will be determined by a random order procedure and will be balanced across the older and younger participant groups. Following an overnight fast, participants will report to the CRC at 0800 when the study will begin with baseline testing and evaluation. MECA or matching placebo will be administered at 0900. NIC or placebo patch will be administered at 1015 and removed immediately before scanning. fMRI scanning will begin at 1100. A double blind, double placebo system will be used. On the days that the MECA pill is active, the NIC patch is placebo and vice versa. Vital signs and pupil diameter will be recorded at 30 min intervals. Cognitive testing during functional neuroimaging will be conducted at 120 minutes after MECA dose and 45 minutes after NIC administration (1100). These times reflect previous data from our group ([name] et al. 2008, 2010; 2012; Carstens et al. 2011; [name] et al. 2009; 2012) on when CNS effects appear to be maximal following administration of nAChR agents. Participants will be transported by a nurse and the experimenter to the MRI suite for the fMRI session that will begin with the functional scans to maximize the drug dose timing. After scanning, participants will return to the CRC, complete mood assessment questionnaires (described below), and will receive lunch. Each participant will be followed until at least 1400, by which time the effects of the nAChR drugs will have dissipated. Participants will be checked for safety using a standard field sobriety test and if their vital signs are within normal limits, will be discharged.

**Figure 7.** Study Day Time Line

**Working Memory Task during fMRI:** Participants will complete a visual verbal **N-back Test** of working memory during the fMRI. This N-back task has three equivalent versions so that a different version will be administered on each study day. The specific version of the task will be counterbalanced across study days for each participant. These versions have been pilot tested with younger and older adults to ensure comparability of different versions and to ensure there is neither ceiling nor floor effects for performance for any age group.

*In this N-back task participants see a string of consonants (except L, W, and Y), presented in upper case letters, one every three seconds. Four conditions are presented: 0-back, 1-back, 2-back, and 3-back. The 0-back control condition had a minimal working memory load; participants are asked to decide if the current letter matches a single target letter that was specified before the epoch begins. In the 1-, 2-, and 3-back conditions, participants indicate whether the current letter on the screen matches a letter that is either 1, 2 or 3 back.*

*The 0-, 1-, 2-, and 3-back conditions are repeated three times in a counterbalanced order such that the same condition is not repeated two times in a row. In this block design task, participants respond to nine items in each block that takes 27 seconds. A rest break follows with a plus sign (+) fixation for 12*

seconds. The total time of the task is 8 minutes 12 seconds. Participants will practice the N-back task before drug dosing on each study day to ensure that they understood task instructions.

**Behavioral Measures:** After the drug challenge and fMRI session, behavioral measures will be completed by the participant and experimenter that have been shown to be sensitive to nicotinic modulation of physical symptoms. Participants will complete the **Profile of Mood States** (POMS) (McNair et al. 1971), a visual analogue battery of items ([name] et al. 1994), a physical symptom checklist, and the **Stanford Sleepiness Scale** (Hoddes et al. 1973), which correlates highly with objective measures of decreased arousal ([name] et al. 1989). The experimenter will complete the **Brief Psychiatric Rating Scale** (BPRS) (Overall and Gorham 1993), a sensitive measure of psychopathologic behaviors that appears to be sensitive to the behavioral changes induced by drugs in normals, and a visual analogue scale ([name] et al. 1994). If group differences are found for these measures, they will be used as covariates in the analyses described below.

**For research involving survey, questionnaires, etc.:** Describe the setting and the mode of administering the instrument and the provisions for maintaining privacy and confidentiality. Include the duration, intervals of administration, and overall length of participation. (describe and attach all instruments)

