### Statistical Analysis

**Analyses for Working Memory Performance Hypothesis Testing (H1a and H2a):** Comparisons of **MECA to placebo** will be conducted in support of **Hypothesis 1a**, while similar analyses comparing **NIC to placebo** will be used to test the hypotheses associated with **Hypothesis 2a**. The overall statistical model is:  $Y_{ijk} = \mu + s_{ik} + \pi_j + \tau_{t[i,j]} + \lambda_{d[i,j-1]} + x_k + \varepsilon_{ijk}$ , where  $Y_{ijk}$  is the value of the outcome of interest (**derived from the performance data described here and imaging data described below**) in subject k in sequence i at period j,  $\mu$  is the overall mean of the outcome of interest;  $s_{ik}$  is the effect of subject k in sequence i,  $i=1, 6$ ;  $\pi_j$  is the effect of period j,  $j=1, 3$ ;  $\tau_{t[i,j]}$  is the effect of treatment t,  $t=1, 2$  in period j of sequence i;  $\lambda_{d[i,j-1]}$  is the carryover effect of the treatment administered in period  $j_1$  of sequence i, where  $\lambda_{d[i,0]}=0$ ;  $x_k$  is the effect of baseline covariates for subject k; and  $\varepsilon_{ijk}$  is the random error (Jones and Kenward 2015). Because of the possibility of missing values in some of the measurements, we will employ a mixed effects model for these analyses, relying on the SAS proc mixed procedure for these analyses (Brown and Prescott, 2006).

**For this model, the effects of  $s_{ik}$  (subject) and  $\varepsilon_{ijk}$  (error) are considered random; all other effects are fixed.**

We will directly examine the effects of the drugs in older adults compared to younger adults. The mixed effects model will be adapted by the inclusion of additional variables to account for the effect of age group ( $g_{il}$  the effect of subject i in age group l; l=younger, older) and the treatment-by-age group interaction ( $g_{il} * \tau_{t[i,j]}$ ). The effect of interest in these analyses will be the interaction, which will test whether the effects of MECA or NIC differ with respect to the age of the subject. We predict there will be a significant interaction and will examine the age differences in response to the challenge drugs. For **performance analyses,  $p<0.05$**  will be used for statistical significance. We have used similar models in our prior work ([name] et al. 2012; [name] et al. 2009).

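### Three N-back versions are rotated over study days, but the crossover model has no version term: a small, avoidable loss of precision

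*Combined protocol and SAP*

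**What the plan says.** The paragraph on the working memory task (Methods and Procedures) states: "This N-back task has three equivalent versions so that a different version will be administered on each study day". On allocation it says: "The specific version of the task will be counterbalanced across study days for each participant". On comparability it says: "These versions have been pilot tested with younger and older adults to ensure comparability of different versions". No version means, standard deviations or differences are reported.

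Drug order is set under Drug Challenge Procedures: "The drug sequence will be determined by a random order procedure and will be balanced across the older and younger participant groups". Version is not mentioned there, and no other section explicitly ties version order to drug or drug sequence.

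The Statistical Analysis section introduces the model with "The overall statistical model is" and lists an overall mean, subject, period, treatment, carryover, a covariate term and error. The covariate term "is the effect of baseline covariates for subject k". For the age comparison, "The mixed effects model will be adapted by the inclusion of additional variables to account for the effect of age group", together with the treatment-by-age interaction. Task version is not among the terms.

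**The concern.** Version changes within a participant from day to day and is deliberately rotated by the design, so it is a design factor of the crossover. None of the listed terms can carry it. The period effect cannot, because versions are rotated over days. The covariate term cannot, because it is indexed by subject and version varies within subject. Any real difference in difficulty between versions therefore stays in the residual.

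At stake is the precision of the treatment-by-age interaction, which is the effect of interest for Hypotheses 1a and 2a. The planned sample size leaves almost no slack on that test. The plan states the same model for the imaging outcomes, so the point carries over to them, but it cannot be put into figures there.

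**Working it through.** **Inputs (Sample Size Calculations).** 3-back proportion correct under placebo is 0.75 in older and 0.88 in younger adults. Under mecamylamine it is assumed to be 0.60 and 0.83. The SD is 0.13, the within-subject correlation 0.35, the type I error rate 0.05 and the target power 90%, with 48 completers per age group. Sidedness is not stated; the two-sided test reproduces the plan's number.

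**1. The plan's own figure.**
- Interaction: (0.75 - 0.60) - (0.88 - 0.83) = 0.15 - 0.05 = 0.10.
- SD of the drug-placebo difference: 0.13 × √(2 × (1 - 0.35)) = 0.1482; variance 0.02197.
- A two-sample comparison of these differences needs 47 per group by the normal approximation and 48 by noncentral t.
- Power with 48 per group is 90.5% (noncentral t). The 48 reproduces per age group; read as a total (24 per group), it gives about 63%. The calculation contains no version component.

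**2. Version order independent of drug order, version omitted.** The documents give no version difference, so d is an assumption: version means at -d, 0 and +d. Each participant receives three different versions, so the two versions behind a drug-placebo difference are drawn without replacement. Each version effect has variance 2d²/3 and each pair has covariance -d²/3. The difference therefore gains 2 × (2d²/3) + 2 × (d²/3) = 2d².

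| d | Added variance 2d² | Rise over 0.02197 | SD of difference | Power, 48 per group | Number per group for 90% |
|---|---|---|---|---|---|
| 0 | 0 | 0 | 0.1482 | 90.5% | 48 |
| 0.02 | 0.0008 | 3.6% | 0.1509 | 89.5% | 49 |
| 0.03 | 0.0018 | 8.2% | 0.1542 | 88.2% | 51 |
| 0.05 | 0.0050 | 22.8% | 0.1642 | 84.0% | 58 |

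**3. Chance shift in the realised trial.** Under the same allocation, the part of the interaction estimate due to drug-version imbalance has mean zero and SD √(2 × 2d²/48). That is 0.0087 at d = 0.03 and 0.0144 at d = 0.05, against an interaction of 0.10. In simulation (2,000 runs per setting, carryover left out) the estimate was centred on the true value, and type I error was 4.2% at d = 0.03 and 5.1% at d = 0.05.

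**4. Version balanced against drug.** The interaction estimate does not shift, and its true standard error stays at 0.1482 × √(2/48) = 0.0303. The residual variance still absorbs the version differences, so the reported standard error is too large. At d = 0.05 it is inflated by √1.228 = 1.108. The effective critical value becomes 1.96 × 1.108 = 2.17, a type I error of about 3.0%. The expected test statistic is 0.10/0.0303 = 3.31, so power is about 87%. Simulation with drug-version pairings matched between the age groups agreed: type I error 3.0%, and power 86.8% without version against 90.6% with it.

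**5. With version in the model.** When version order is independent of drug order, simulated power returns to about 90%: at d = 0.03, 89.8% against 88.4% without the term; at d = 0.05, 90.0% against 84.0%. If the versions are truly equal, the term costs about 0.3 points (90.2% against 90.5%).

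**6. Whether 48 per group permits exact balance.** Write P, M, N for placebo, mecamylamine and nicotine, and A, B, C for the versions. Pair drug and version orders as PMN-ABC, PNM-ACB, MPN-CBA, MNP-CAB, NPM-BCA, NMP-BAC. Each of the nine drug-version pairs then occurs twice, and each version occurs twice on each day. Eight such sets of six make 48 participants, with each drug-version pair occurring 48/3 = 16 times.

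**The case against.** The strongest reply is that the versions are described as equivalent and were pilot tested in both age groups, so leaving version out is a defensible choice. The d = 0.05 case puts the easiest and hardest versions 0.10 apart, as much as the whole planned interaction, which sits badly with that description. At d = 0.02 the loss is about one power point. The loss may also be partly counted already: if the pilot data behind the correlation of 0.35 came from rotated versions, which the plan does not say, version variance is already in the planning figures.

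Much of this stands, and it keeps the point small. It does not remove it, because no pilot figures are given and small differences are hard to exclude. With the plan's own SD and correlation, a 95% interval of ±0.03 on a version difference needs (1.96 × 0.1482/0.03)², about 94 people; ±0.05 needs about 34.

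It can also be said that study days here are the drug conditions, so counterbalancing across them may already cover drug. That reading is possible. It removes the chance shift (step 3) but leaves the conservative test (step 4).

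A reader might infer two stronger points. The first is that drug and version cannot be exactly balanced because 48 does not divide evenly over all combinations of drug order and version order. Balance does not require filling every combination, and step 6 shows an exact arrangement. The second is that the drug effect is biased. The documents do not support that: nothing links particular versions to particular drugs, and over repeated trials the estimate is centred on the truth.

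**Conclusion.** The omission is real and minor. The design rotates three versions, and no term in the stated model can absorb differences between them. The consequence is lost precision, plus a chance shift in the realised trial if version order is independent of drug order, or a conservative test if it is balanced against drug. There is no systematic bias, and type I error is not inflated.

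The size depends on an assumed version difference: about 1 power point at d = 0.02, 2.3 at d = 0.03 and 6.5 at d = 0.05, when version order is independent of drug order. These figures take the planning SD and correlation as free of version variance. The documents do not show that the versions differ, nor that drug and version will be unbalanced; they leave both open.

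**What to change.** Add task version (three levels) to the mixed model as a fixed within-subject effect, for the performance outcomes and wherever the same model is used for imaging. State that version order is balanced against drug sequence within each age group, for example with the six pairings in step 6 repeated eight times. Keep the model term even with balanced allocation: the expected dropout of about 20% can break the balance, and without the term the test stays conservative.

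The cost is two degrees of freedom (about 0.3 power points if the versions are truly equal), an allocation list that carries both drug and version order, and a record of the version used each day. The documents do not say that this is recorded, so the plan should require it.
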